The Effect of Early Saline Lavage on Synovial Fluid Composition Following Human
Intra-Articular Ankle Fracture

Document Date: 12/12/2024

NCT05465382

Purpose of the Study

The purpose of this study is to examine the effect of early, percutaneous, intra-articular saline lavage on the undiluted synovial fluid microenvironment during the acute phase following intra-articular fracture of the human ankle. We hypothesize that early intervention with percutaneous joint lavage in the first 0-48 hours after injury will attenuate the production of pro-inflammatory cytokines, MMP's and cartilage breakdown products compared to non-lavaged control subjects at the time of surgical fixation.

Background & Significance

Post traumatic osteoarthritis (PTOA) is a frequent cause of disability in orthopaedic trauma patients. Post-traumatic etiologies represent a disproportionately high percentage of clinically significant osteoarthritis of the ankle (65-80%) as compared to the knee and hip (2-10%). Compared to other forms of arthritis, PTOA is unique in that the timing of onset is known. As a result, there is an opportunity for studying the underlying pathogenesis at the time of injury and targeting interventions aimed at treating early disease and preventing disease progression.

Traditionally, the intraoperative restoration of anatomic joint congruity and balanced articular loading were thought to be the main factors involved in preventing the development of PTOA. However, even after anatomic reduction, intra-articular fractures of the lower extremity are still susceptible to the development of PTOA. Furthermore, the relationship between residual articular surface displacement and the development of PTOA is inconsistent in the literature. While the mechanical components of intra-articular fracture treatment have been well studied, more recent work has focused on better understanding the biological response within the joint that likely contributes to cartilage damage and the progression of PTOA.

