As described above, this study represents minimal risk and discomfort to subjects. It is standard of care to administer an intra-articular lidocaine injection during the emergency department management of ankle fractures. We will utilize this standard of care needle insertion to the fractured ankle to perform our study related aspiration and saline lavage. In this way, no additional risk or discomfort will be incurred by the subject as a result of participation. Patients choosing not to participate will receive the normal standard of care for treatment of their injury independent of this study. Furthermore, consenting to participate in this study in no way obligates subjects to undergo surgical fixation of their ankle fracture. This decision will be made in consultation with their treating surgeon.

Risk is involved to the extent that privacy and confidentiality may be compromised. However, every reasonable effort will be made to limit breaches of privacy and confidentiality.

Subjects will not benefit directly from this study. However, data and conclusions derived from this study may improve the current understanding of post traumatic arthritis and possibly influence future patient care or study designs.

Data Analysis & Statistical Considerations

Sample Size Estimate

The study was powered (a-priori) for randomized between group differences in the primary outcome measures of Cytokines and Matrix Metalloproteinase levels collected during standardized aspirations. The study will involve two independent groups: 1) individuals with intra-articular fractures of the ankle who receive saline lavage (experimental) and 2) individuals with intra-articular fractures of the ankle who do not receive lavage (control). Differences between groups will be evaluated with a fixed effects repeated measures, analysis of covariance (RM-ANCOVA) with three dedicated time points ([1.] baseline, [2.] in the OR after anesthesia is induced (generally within 24 hours of lavage), and [3] 1 to 2 weeks post-injury). Baseline cytokines and Matrix Metalloproteinase levels will be used as a covariate control. Assuming a normal distribution for the cytokines and Matrix Metalloproteinase levels and assuming a partial theta squared effect size of 0.40 (large effect*, primarily occurring at the second time

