point), we constructed a sample size estimation estimating for between groups' comparisons. With an expected 80% power, 2 time intervals*, 1 control interval, two independent groups, and a standard error of probability of 0.05, we estimated the need for a minimum sample size of 40 for statistical significance (~20 per group). We will employ intention to treat and chains equation imputation and will not oversample each group for drop outs.

Statistical Analyses

The primary outcome measure will be cytokines and Matrix Metalloproteinase levels measured at two distinct time points after injury. We will use a between groups, repeated measures Analysis of Covariance (RM-ANCOVA) to measure differences between the two designated groups. A RM-ANCOVA is used in examining the differences in the mean values of the dependent variables that are related to the effect of the controlled independent variables while taking into account the influence of the uncontrolled independent variables (baseline) over more than one time point. A p value of 0.05 will be used to measure statistical significance.

*Medium effect size required a sample size of 98

+Three time intervals would only require a sample size of 36.

Data & Safety Monitoring

The only major risk involved is the loss of confidentiality and every effort will be made to ensure this does not happen by the research staff. No followup contact with subjects will be necessary after their ankle aspirations. The results of this research will not be placed in their medical record. No PHI will leave Duke. It will not be necessary to specifically provide the subjects with any additional information, as their involvement ends with their ankle joint aspiration at the time of surgery and does not influence their longitudinal care. Furthermore, any research findings will be made available through publication. Research records containing MRN will be kept in an electronic spreadsheet on the Duke server of which access is limited to the PI and his research staff. Any electronic information will be stored on a computer that is password protected. After data collection and prior to statistical analysis, a case number will be assigned to the data and the medical record number (the only identifying data collected) will be stripped from the database. After the review is complete, publication has been accepted and all revisions have been made to the manuscript, then the study will be closed in the eIRB.

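### The primary outcome is an unlisted set of cytokines and MMPs judged at an unadjusted 0.05, with no primary analyte or success rule, while the sample size is for one test

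*Combined protocol and SAP*

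**What the plan says.** Under Purpose of the Study, the hypothesis is directional and covers three classes of analyte: early lavage "will attenuate the production of pro-inflammatory cytokines, MMP's and cartilage breakdown products" relative to controls at surgical fixation.

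Under Sample Size Estimate, the trial is powered for "primary outcome measures of Cytokines and Matrix Metalloproteinase levels collected during standardized aspirations". The calculation is described as "With an expected 80% power, 2 time intervals*, 1 control interval, two independent groups" and "a standard error of probability of 0.05", with an effect size of 0.40. It gives a minimum of 40 subjects, about 20 per group. Footnotes give 98 for a medium effect and 36 for three time intervals.

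Under Statistical Analyses, the outcome is again two plural classes: "The primary outcome measure will be cytokines and Matrix Metalloproteinase levels measured at two distinct time points after injury". The method is a between-groups RM-ANCOVA, and the only decision rule is "A p value of 0.05 will be used to measure statistical significance".

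No section lists the analytes, ranks them, combines them, says how many must differ, or mentions adjustment. Nothing suggests that such text was redacted.

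**The concern.** A primary outcome made of several analytes needs a rule that turns several p-values into one conclusion. This plan gives a threshold but no such rule. RM-ANCOVA as described has time as its repeated factor and does not combine analytes, so the natural way to follow the plan is one model per analyte, each compared with 0.05. Nothing then prevents a single significant analyte from being reported as support for the hypothesis, or the analytes to emphasise from being chosen after the results are seen.

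Two things are at stake. The error rate of the primary claim is not controlled, and the stated 80% power belongs to one test rather than to any claim about the panel.

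A separate gap is that cartilage breakdown products are in the hypothesis but in neither the sample size nor the analysis text. This is an omission, not a type I error problem.

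**Working it through.** **1. What the stated sample size covers.** Inputs from Sample Size Estimate: effect 0.40, two groups, m = 2 post-baseline measures, alpha 0.05, power 80%. Assumed: correlation ρ = 0.5 between repeated measures, which is not stated. For the between-groups F test, λ = f²·N·m / [1 + (m − 1)ρ] with df (1, N − 2).

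- f = 0.40, m = 2, N = 40: λ = 0.16 × 40 × 2 / 1.5 = 8.53, power 0.812.
- f = 0.25 (medium), m = 2, N = 98: λ = 0.0625 × 98 × 2 / 1.5 = 8.17, power 0.808.
- f = 0.40, m = 3, N = 36: λ = 0.16 × 36 × 3 / 2 = 8.64, power 0.815.

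All three stated figures (40, 98 and 36) reproduce as the smallest even N reaching 80%, each for one test at 0.05. They do so only if 0.40 is Cohen's f. Read as a partial eta squared, f = √(0.4/0.6) = 0.816 and N would be 12. The label needs correcting, but this does not affect the multiplicity point.

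**2. False-positive rate if any one analyte counts as success.** Panel size k is not stated. Two plural classes imply at least 2 + 2 = 4 if taken literally; 10 and 20 are assumed larger panels, and k = 2 is shown as a floor. For independent analytes the rate is 1 − 0.95^k in either direction and 1 − 0.975^k in the benefit direction. For correlated analytes, k equicorrelated normal statistics were simulated with 400,000 draws.

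| k | Either direction, corr. 0 | 0.5 | 0.9 | Benefit only, corr. 0 | 0.5 | 0.9 |
|---|---|---|---|---|---|---|
| 2 | 9.8% | 9.1% | 7.1% | 4.9% | 4.5% | 3.5% |
| 4 | 18.5% | 15.6% | 9.4% | 9.6% | 7.8% | 4.7% |
| 10 | 40.1% | 28.7% | 12.7% | 22.4% | 14.4% | 6.4% |
| 20 | 64.2% | 41.9% | 15.4% | 39.7% | 21.1% | 7.7% |

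The nominal levels are 5% and 2.5%. Testing the two time points separately would raise these rates further.

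**3. Power after adjustment.** Same f, m and ρ, with Bonferroni at 0.05/k:

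| k | Per-analyte power, N = 40 | Per-analyte power, N = 60 | Total N for 80% per analyte |
|---|---|---|---|
| 1 | 0.81 | 0.94 | 40 |
| 4 | 0.62 | 0.84 | 56 |
| 10 | 0.49 | 0.74 | 68 |
| 20 | 0.39 | 0.66 | 76 |

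With one df spent on the baseline covariate, the k = 10, N = 40 entry is 0.484.

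Per-analyte power is not the power to detect at least one analyte. By simulation with N = 40, k = 10, d = 0.8 for each responding analyte (λ = 8.53) and inter-analyte correlation 0.5:

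| Analytes responding | At least one, Bonferroni | Equal-weight composite at 0.05 |
|---|---|---|
| 10 of 10 | about 90% | about 97% |
| 5 of 10 | about 82-85% | about 48% |

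**4. Which samples the test would use.** Sample Size Estimate lists two post-baseline time points: in the operating room, generally within 24 hours of lavage, and at 1 to 2 weeks post-injury. Design & Procedures describes one post-baseline aspiration, at surgery, and Data & Safety Monitoring says involvement ends with it. These sections disagree.

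**The case against.** The strongest reply is that the plan never says each analyte is tested separately, or that one significant result is enough. The hypothesis joins its classes with a conjunction, and a reader who required every class to differ would face no such inflation. This stands as far as it goes: the success rule is undefined, and reading any one analyte as success is an inference. It does not rescue the plan, because an undefined rule cannot control error.

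A reader might infer that the chance of wrongly concluding that lavage works is 40% or 64%. The documents do not support that. Those figures assume independent analytes and panels of 10 or 20, and they count analytes that are falsely worse after lavage, which would contradict a hypothesis of attenuation. Limited to the benefit direction at correlation 0.9, the figures are 6.4% and 7.7% against 2.5%.

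A reader might also infer from the 48-49% power that adjusting across the panel is unworkable and that a composite is clearly better. That figure is power per analyte. Power to detect at least one remains near 90% if all ten respond, and the composite does much worse if only half do.

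Finally, this is a small single-centre biomarker study. But it is presented as a randomised trial with a directional hypothesis, an a-priori power calculation and a declared primary outcome, so an exploratory reading does not remove the need for a rule.

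**Conclusion.** The concern holds. The primary outcome is an unlisted set of analytes with one unadjusted 0.05 threshold and no primary analyte, global test, success rule or multiplicity control, and N = 40 at 80% power is for one test. That rests on the text alone.

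The size of the inflation is conditional on any one significant analyte being read as success and on assumed panel sizes of 4 to 20 and correlations of 0 to 0.9. Under those assumptions the rate is above nominal in every case: about two to thirteen times 5% in either direction (9.4% to 64.2%), and about two to sixteen times 2.5% in the benefit direction (4.7% to 39.7%). No single figure can be given. The sponsor should settle this before any assay results are seen.

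**What to change.** First reconcile the number and timing of post-baseline aspirations across Design & Procedures, Sample Size Estimate and Data & Safety Monitoring, so that the primary test uses samples that will exist.

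Then, before the batch assay, fix the analyte list and state one primary rule with overall error 0.05. Any of these would do:

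- Holm adjustment across the listed cytokines and MMPs, stating what counts as success.
- One named primary analyte at 0.05, which keeps N = 40 under the plan's own assumptions.
- One pre-specified composite or global test at 0.05.

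Under the second and third options, the individual analytes not used for the primary claim become secondary, with adjusted p-values. Under all three, add the cartilage breakdown products as an adjusted secondary outcome. State that 80% power at N = 40 applies to a single test; if a per-analyte claim is wanted under adjustment, redo the sample size.

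The multiplicity change itself needs only plan wording and a fixed list, because the aspirates are frozen for batch analysis; it needs no extra patients or procedures unless per-analyte power is to be restored. The downsides are larger adjusted p-values for single analytes and, for an equal-weight composite, loss of power if only some analytes respond.
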